6.1 Clinical Evaluation after Imaging

The clinician will be serially unblinded to MRI and PET data *in the following sequence* for each patient; this need not be done during an actual patient recheck. The clinician shall remain blinded to the QREADS radiology report. Qualitative scores are used for PET since the MRI scale is qualitative and since quantitative cut-off values for SUV-max do not currently exist:

1. Unblinded to facet joints positive for high-grade MRI change based on overall scores
2. Unblinded to all positive facet joints on MRI based on overall scores (low grade and high grade)
3. Unblinded to facet joints positive for marked FDG PET activity based on qualitative scores
4. Unblinded to all positive facet joints on FDG PET based on qualitative scores (low grade and high grade)

For each of these 4 iterations, the clinician will score if:

1. The data is concordant or discordant with the clinical impression (dichotomous yes/no)
2. The data would change clinical management (dichotomous yes/no)

These 2 scores will be performed with the assumption the biomarker is an accurate predictor of facet joint pain and/or response to percutaneous treatment. Without this assumption, the results would have no impact on management. This will be done independently on each side per patient.

Note that the results could be concordant with clinical impression, but still alter management (for example clinically suspected left L5/S1 facet joint pain with a positive biomarker at only the left L4/L5 facet joint).

Finally, the clinician will indicate which facet joint(s) he/she would specifically prescribe percutaneous treatment for using both clinical and all available PET/MRI data. Note that the PET/MRI data is not an absolute determinant here. The clinician may believe strongly that a facet joint should undergo percutaneous treatment based on clinical data alone.

The actual clinical management is left to the discretion of the clinician for this phase of evaluation. He/she may choose to treat the patient based on clinical information alone or clinical and PET/MRI information. The clinical course including level of pain, response to injections, etc. of the patients may be followed up to 1 year after the PET/MR by chart review for descriptive purposes/analysis, but the patients will not be formally contacted.

6.2 Primary Data Analysis

1. The concordance of qualitative scores of FDG activity with clinical impression will be determined (high grade and all grades).
2. The concordance of overall scores of MR findings with clinical impression will be determined (high grade and all grades).
3. The frequency with which the qualitative scores of FDG activity altered clinical management will be scored (high grade and all grades).
4. The frequency with which the overall scores of MR findings altered clinical management will be scored (high grade and all grades).
5. For each patient, the number (and level) of facet joints prescribed percutaneous treatment will be determined in these 3 categories:
 - a. Number of facet joints with unchanged treatment recommendation
 - b. Number of new facet joints that would be treated with PET/MR data
 - c. Number of facet joints initially prescribed treatment based on clinical exam that would not undergo percutaneous treatment with PET/MR data.
6. The degree of concordance of FDG PET activity and MRI findings will be scored.
7. The frequency of upgrading the overall score with gadolinium images versus T2 images alone will be determined.
8. The frequency of pure facet joint synovial enhancement or effusion without peri-facet signal change will be determined.

9. Qualitative FDG PET scores will be compared to SUV-max scores (absolute and as a ratio to normal vertebral body activity) to determine if quantitative thresholds can be established for future investigation.
10. The concordance of DWI results with other imaging findings and clinical data will be assessed for exploratory purposes.
11. Interobserver variability for both FDG PET scores and MRI scores will be examined.

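### Section 6.2 items 5b and 5c are before/after counts: no reason is recorded for a changed joint, so they cannot be attributed to imaging or divided between MRI and PET

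*Combined protocol and SAP*

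**What the plan says.** Section 5 item 5 has the clinician record, once and before the scan, which facet joints are to be treated percutaneously. Item 7 allows the scan up to 3 months later.

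Section 6.1 then discloses results in four steps: high-grade MRI, all positive MRI, marked PET, all positive PET. At each step the clinician gives two yes/no scores. One is agreement with the clinical impression. The other is "The data would change clinical management (dichotomous yes/no"), called the management score below. On both scores, 6.1 says: "These 2 scores will be performed with the assumption the biomarker is an accurate predictor of facet joint pain". On the unit of scoring it says: "This will be done independently on each side per patient".

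After the fourth step, "the clinician will indicate which facet joint(s) he/she would specifically prescribe percutaneous treatment for using both clinical and all available PET/MRI data". The section adds: "Note that the PET/MRI data is not an absolute determinant here". It also adds: "The clinician may believe strongly that a facet joint should undergo percutaneous treatment based on clinical data alone".

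Section 6.2 item 5 sorts joints into those with an unchanged recommendation (5a), the "Number of new facet joints that would be treated with PET/MR data" (5b), and the "Number of facet joints initially prescribed treatment based on clinical exam that would not undergo percutaneous treatment with PET/MR data" (5c).

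**The concern.** Every added joint falls in 5b and every dropped joint in 5c, and both labels refer to PET/MR data. The final list, however, rests on clinical and imaging information together, and nothing on the form says which of the two moved a given joint. The only reasons the protocol asks anyone to document are those for disagreement between image readers.

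This matters because item 5 is the only primary-analysis item that counts which joints would gain or lose treatment. Section 3 says the study should help show whether the biomarkers could change management and should inform a larger study. The opening background adds that the best biomarker or biomarkers have to be selected. A reader of 5b and 5c would want to know how much of the change came from imaging, and from which modality. As planned, the counts cannot answer either question.

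**Working it through.** The plan gives no figure for this point, so there is none to reproduce. The check sets out what is recorded and how far it can separate the causes of a change.

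**Inputs.** 10 enrolled patients (end of section 2). 5 levels, L1/L2 to L5/S1 (section 6, MRI item 10), on 2 sides. 4 disclosures (6.1). Treatment is usually prescribed to the 4 lowest joints (opening background).

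**Counts.**
- Joint decisions: 10 × 5 × 2 = 100, or 10 × 4 = 40 if only the usual four joints are in play.
- Sides: 10 × 2 = 20. Management scores: 20 × 4 = 80.
- Joints covered by one management score: 5, or 2 of the usual 4.

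**What the existing data can separate.** Take three facts about a changed joint: added or dropped; its MRI and PET ratings; and whether its side was scored yes at least once or no at all four disclosures.

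1. With imaging reduced to positive or negative, there are 2 × 2 × 2 = 8 patterns. All 4 on no sides are unexplained by imaging. On yes sides, an added negative joint and a dropped positive joint are at odds with imaging. That flags 4 + 2 = 6. The 2 left open are added, positive, yes; and dropped, negative, yes. A true imaging effect would produce exactly these two.
2. With MRI and PET kept apart there are 4 rating patterns, so 2 × 4 × 2 = 16. All 8 on no sides are flagged. On yes sides only 2 are flagged: added with both ratings negative, and dropped with both positive. That flags 8 + 2 = 10 and leaves 16 − 10 = 6 open, including every MRI/PET-discordant pattern on a yes side.

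These are counts of patterns, not shares of joints. The documents do not say how often each would occur.

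**Why a yes does not settle it.** Section 6.1 gives its own example: left L5/S1 is suspected, only left L4/L5 is positive, and this counts as altering management. The left side is therefore scored yes. If an imaging-negative left L3/L4 were also dropped for a clinical reason, it would look the same as a joint dropped because of imaging. In addition, the management score supposes an accurate biomarker, and that condition is not attached to the final list. A yes therefore does not show that imaging moved the final list.

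**Could a change have another cause?** Three features leave room for it. The scan may follow the assessment by up to 3 months. A patient recheck is not required but is not excluded. Section 5 names three possible examiners, and 6.1 speaks only of the clinician without saying that the same one makes both lists. None of this shows that such changes will occur.

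**The case against.** The strongest reply is that item 5 makes no causal claim. The 'with' in both labels can mean 'once the data are available', matching how 6.1 builds the final list. On that reading 5a to 5c are a plain before/after tally. This stands: a reader might infer that item 5 contradicts 6.1, and the documents do not support that. The gap is in attribution.

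Second, a reader might take the sentence on treating from clinical data alone as evidence that joints are added or dropped for clinical reasons. It most naturally describes a joint kept despite negative imaging, which falls in 5a. It speaks of treating a joint, so it can bear on 5b but lends no support for 5c. For 5c the case rests on the mixed information behind the final list and the missing reason.

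Third, without a required recheck there may be little new clinical information. What remains is a clinician deciding again, and the documents give no estimate of how often that alters a list. This also stands.

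Fourth, the existing data already do much of the separating, and the disclosures run by modality, so a side scored yes only at the PET steps points towards PET. This is right as far as it goes. But the clinician has already seen MRI by then, each score still spans five joints, and 6.2 plans no cross-tabulation.

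Finally, items 3 and 4 already report management change by modality and grade, so Aim 1 does not rest on item 5. That is true, but they answer per side and do not say which joints change.

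**Conclusion.** The concern holds as an attribution gap. As planned, 5b and 5c describe how the list changed between two dates. They cannot say how much of the change is due to imaging, or to MRI rather than PET. Existing data narrow this but leave open 6 of 16 patterns, including those a real imaging effect would produce.

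The number of non-imaging changes cannot be derived from the documents and may be near zero, so it would go too far to say that the counts are inflated by any particular amount. Items 3 and 4 are little affected. In a 10-patient exploratory study without a stated hypothesis test, this is a cheap improvement and not a flaw that undermines the study. The conclusion assumes that readers will want to use item 5 to judge the effect of imaging on joint selection, as section 3 suggests.

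**What to change.** 1. In 6.1, when the final list is made and with the original list in view, record for each added or dropped joint whether the reason was MRI, PET or clinical, allowing more than one.
2. Keep the initial examination-based list as the comparator. Item 5c is defined against it, and it predates the scan. Report 5b and 5c split by recorded reason, cross-tabulated with the per-joint MRI and PET ratings and with the side-level scores at each disclosure.
3. In 6.2, describe total 5b and 5c as before/after changes, and attribute to imaging only the part with an imaging reason.

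Items 3 and 4 stay as they are, and sample size and imaging do not change. The cost is a short form for each of 10 patients and a few lines of text. The stated reasons are the clinician's own view, which is why the cross-tabulation is needed. They should be captured when the list is made, because they cannot be reliably reconstructed later.

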2. Determine the approximate frequency of each independently studied imaging biomarker to facilitate power calculations.
3. Determine if FDG PET activity and MR biomarkers are highly correlated and thus potential surrogates, or if these are discrepant and possibly complementary.
4. Perform an exploratory evaluation of DWI for assessment of facet joints.
5. Assess the concordance of findings on gadolinium enhanced MRI with T2 fat-suppressed MRI using both axial and sagittal images to determine if gadolinium administration will be necessary for future clinical investigation.

We plan to screen up to 40 patients to ensure we enroll 10 subjects.

3. Hypothesis/Study Category:

This is an exploratory study investigating the utility of FDG PET activity and MRI signal change around facet joints in the clinical management of low back pain. This study will help determine if such imaging biomarkers could change clinical management. Additionally, this will provide data that will be vital to planning a larger prospective study evaluating the ability of imaging biomarkers to predict response to comparison medial branch blocks and RF ablation for treatment of facet joint pain. Such a prospective study could not be adequately designed without this initial exploratory component.

4. Methodology

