7. After each group of up to 5 studies (or fewer), the 2 readers will re-review the studies together to establish consensus and document reasons for interobserver variability.
8. The consensus facet joint scores will then be grouped into 3 categories for comparison to PET data and clinical translation: 1 = normal (0/4), 2= mild peri-facet signal change (1-2/4), 3 = high grade peri-facet signal change (3-4/4).
9. After each group of 5 studies, the 2 readers will re-review the studies together to establish consensus and identify/document reasons for interobserver variability (if any).
10. The overall score for each lumbar facet joint (L1/L2 through L5/S1) will represent the highest of the 2 consensus grades (of T2 fatsat and T1 fatsat with gad).

PET Images

1. Patients will receive a routine clinical dose of F18 FDG and undergo PET imaging at a standard recorded interval.
2. Every lumbar facet joint will be rated as either normal or having increased activity on qualitative visual inspection independently by 2 nuclear medicine physicians on a scale of normal, mildly increased, or markedly increased (high grade).
3. Maximum standard uptake value (SUV-max) will also be determined and will be compared to the SUV-max of the adjacent normal vertebral body (avoiding areas increased in association with degenerative disc disease).
4. The PET readers can view anatomic T1 images for coregistration, but will be blinded to the fat-suppressed MR images/results.
5. After each group of up to 5 studies (or fewer), the 2 readers will re-review the studies together to establish consensus and identify/document reasons for interobserver variability (if any).
6. The consensus rating by visual inspection will establish the qualitative score.

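### Aim 5 asks for T2–gadolinium concordance, but the only planned grade comparison counts upgrades of a maximum and so cannot give it; cross-tabulate the two grades already recorded

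*Combined protocol and SAP*

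**What the plan says.** Section 2 (Specific Aims), aim 5, is to "Assess the concordance of findings on gadolinium enhanced MRI with T2 fat-suppressed MRI". Its stated purpose is "to determine if gadolinium administration will be necessary for future clinical investigation". On size, the same section says "We plan to screen up to 40 patients to ensure we enroll 10 subjects".

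Section 6 (Image Analysis, MRI Images) has two neuroradiologists grade every lumbar facet joint from 0 to 4, first on T2 fat-suppressed images (item 2) and then on gadolinium-enhanced T1 fat-suppressed images (item 3). Item 2 masks the T2 read to the gadolinium images. Item 3 is silent on whether the gadolinium read is masked to the T2 grades. After consensus, item 10 says the overall score for each joint "will represent the highest of the 2 consensus grades (of T2 fatsat and T1 fatsat with gad". Item 8 adds a coarser scale: "The consensus facet joint scores will then be grouped into 3 categories for comparison to PET data and clinical translation". Section 6.1 shows the clinician results by that coarser grading, starting with "Unblinded to facet joints positive for high-grade MRI change based on overall scores".

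In section 6.2 the T2 and gadolinium grades are compared only in item 7: "The frequency of upgrading the overall score with gadolinium images versus T2 images alone will be determined". The nearest neighbours are item 8, "The frequency of pure facet joint synovial enhancement or effusion without peri-facet signal change will be determined", and item 11, which covers differences between readers. Neither sets the T2 grade against the gadolinium grade.

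**The concern.** The aim names one quantity and the analysis delivers another. Because the overall score is a maximum, it can never fall below the T2 grade. Item 7 can therefore show only no change or a gain. A joint graded 3 on T2 and 1 on gadolinium disagrees by two grades, yet it falls in the same cell as a joint graded 3 on both. Agreement cannot be recovered from the reported count.

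This matters for how the count is read. If the two sequences carry the same information and each is graded with some error, upgrades still occur. An appreciable count might then be taken as a reason to keep gadolinium when it is largely reading variation, or dismissed as noise when it is a real gain. Item 7 also does not say whether an upgrade is counted on the 0–4 scale or on the three categories, and the frequency expected from noise differs between them.

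**Working it through.** The plan gives no expected agreement, error rate or grade distribution, so there is no figure of its own to reproduce. Part of the argument is pure logic, and the rest uses stated assumptions.

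**Logic (no assumptions).** Overall = max(T2, gadolinium) ≥ T2. Item 7 counts joints with gadolinium > T2. Joints with gadolinium = T2 and gadolinium < T2 are pooled. Exact agreement = 1 − P(up) − P(down), and P(down) is not reported.

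**Number of joints.** 10 patients × 5 levels (L1/L2 to L5/S1) × 2 sides = 100, if all are readable.

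**Upgrades expected with no gain.** With equivalent sequences and exchangeable error, P(up) = P(down) = (1 − agreement)/2.

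| Assumed exact agreement | P(up) | Upgrades in 100 joints |
|---|---|---|
| 90% | 0.10/2 = 0.05 | 5 |
| 80% | 0.20/2 = 0.10 | 10 |
| 70% | 0.30/2 = 0.15 | 15 |

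**Dependence on the scale.** Assume true grades 0–4 in 50/20/15/10/5% of joints, and independent reads that err by one grade up or down with probability e/2 each, truncated at 0 and 4. For e = 0.2:
- Misgraded per sequence: 0.45 × 0.2 + 0.55 × 0.1 = 14.5%.
- Upgrades on 0–4: 0.45 × (0.1 × 0.9 + 0.8 × 0.1) + 0.55 × (0.9 × 0.1) = 0.0765 + 0.0495 = 12.6%.

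Over e = 0.1 to 0.3, upgrades from noise alone are 6.8–17.5% on 0–4, 4.5–12.1% on three categories and 1.2–3.2% into high grade. Over three assumed grade mixes the ranges are 6.0–19.1%, 4.3–12.5% and 0.6–4.5%.

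**What the full table adds, and what it does not.** Three assumed scenarios, all with the first grade mix:
- A: no gain; 14.5% of joints misgraded per sequence.
- B: gadolinium truly one grade higher in about 10% of joints; 3.6% misgraded.
- C: gadolinium truly one grade higher in about 11% and truly one grade lower in about 12%; 1.5% misgraded.

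| | A | B | C |
|---|---|---|---|
| Up / down, 0–4 (%) | 12.6 / 12.6 | 12.2 / 3.2 | 12.2 / 12.8 |
| Up / down, three categories (%) | 8.6 / 8.6 | 8.4 / 2.1 | 8.4 / 7.9 |
| Into / out of high grade (%) | 2.3 / 2.3 | 2.0 / 0.5 | 2.0 / 2.6 |
| Exact agreement, 0–4 | 0.748 | 0.846 | 0.750 |
| Linear weighted kappa | 0.80 | 0.88 | 0.80 |

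Item 7 sees only the upgrades, which are nearly equal in all three. The table sets B apart from A. It does not set C apart from A.

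**Precision.** Effective n = 100/(1 + 9 × ICC), which is 52.6 at an assumed within-patient correlation of 0.1 and 27.0 at 0.3. With u and d the upgrade and downgrade proportions, net shift has variance (u + d − (u − d)²)/n.
- A, ICC 0.1: 0 ± 1.96 × √(0.252/52.6) = 0 ± 13.6 points.
- B, ICC 0.1: 9.0 points (−1.3 to 19.3).
- At ICC 0.3: A is 0 ± 18.9 and B is 9.0 (−5.4 to 23.4).
- Zero upgrades would still leave a Wilson upper 95% limit of 6.8% (ICC 0.1) or 12.4% (ICC 0.3).

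**The case against.** The strongest reply is that item 7 fits the decision. With the overall score defined as the higher grade, upgraded joints are exactly those whose score would change if gadolinium were dropped, and a near-zero count would support omitting it. That stands, and it is why the count should be kept. It does not turn the count into the concordance that aim 5 names.

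A reader might infer that counting downgrades would separate real gain from reading variation. The documents do not support that. A joint may truly show T2 signal without enhancement, and such joints are downgrades too. Scenario C, where gadolinium does add true findings, is almost indistinguishable from the pure-noise scenario A. No repeat reads are planned, and between-reader variability (item 11) is only a partial yardstick for error.

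The exchangeable-error premise is also open to challenge. Nothing provides for separate readers for the two sequences, T2 is graded first, and masking is stated for that read only. Carry-over would correlate the errors, lower the noise-only upgrade rate and suppress downgrades. Consensus grading may also leave less error than assumed here. These points stand and limit what the table can show.

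On scale, 0–4 is a reasonable reading, since item 10 speaks of grades and item 8 ties the three categories to PET comparison and clinical translation. It is still not stated.

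Finally, the intervals for A and B overlap and both include zero, so the table cannot be a test. Both grades are recorded, so it could also be made later.

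**Conclusion.** The mismatch holds. Aim 5 asks for concordance, and the one planned comparison of the two grades cannot supply it, because downgrades are pooled with agreement. This follows from the scoring rule alone. That some upgrades are expected without any gain follows if errors are exchangeable; the size (5 to 15 joints in about 100) rests on assumed agreement of 90% to 70%. The grade mixes, error rates, true differences and within-patient correlations are likewise assumptions, since the documents give none.

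Two stronger readings should not be drawn. The upgrade count is not uninformative: it bears directly on dropping gadolinium. Nor would the fuller table settle the cause of disagreement: it shows agreement and asymmetry, and a net shift near zero is not by itself evidence that gadolinium adds nothing. No information is lost for good either. This is a cheap improvement of low-to-moderate importance for a 10-patient exploratory study.

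**What to change.** Keep the upgrade frequency and add to section 6.2, item 7:

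*Consensus T2 and gadolinium grades will be cross-tabulated per joint (0–4 and three-category), and exact agreement, weighted kappa, upgrades, downgrades and net shift will be reported descriptively, listed by patient, with any intervals allowing for clustering of joints within patient.*

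Add two statements alongside it:
- In section 6, MRI Images, item 3: whether the gadolinium read is masked to the T2 grades, because carry-over would suppress downgrades.
- In section 6.2: that downgrades may be reading variation or true T2-only signal, so the table does not identify the cause of disagreement, and that item 11 is only a partial guide to reading error.

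The cost is slightly more analysis, with no new patients, scans, readers or reading sessions. The downside is wide intervals, including an imprecise kappa, with 10 patients. Planning it now fixes the scale and the summaries before the results are seen.
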